### 5.3 Subject Recruitment

There will be three available recruitment sources for the study. The first will be existing tinnitus patients cared for by Otorhinolaryngology providers. The second will be patients being referred for tinnitus to the Department of Otorhinolaryngology. These patients will be identified by the appointment coordinators, consulting team, investigator, or study coordinator. The third group are people who have contacted the study team to participate in a tinnitus related research study at Mayo Clinic, after having seen a posting on ClinicalTrials.gov or the Mayo Clinic website. The study team may then contact the subject with a letter mentioning the prospective trial and will provide study team contact number to obtain more information. All members of the clinic team, including consultants, residents, audiologists, and nurses will be made aware of this study's inclusion and exclusion criteria and will identify appropriate patients. Consent to participate in the study will be obtained at the time of consultation. Alternatively, subjects may be contacted by phone or video to review the inclusion and exclusion criteria, with the potential of being consented by phone or video and either signing the consent form electronically or by mail, if the subject can't or doesn't want to sign electronically.

#### **5.4 Withdrawal of Subjects**

Patients who are not able to be evaluated on the date of appointment or those who should choose to withdraw for any reason will have the option to withdraw at any time.

## 6 STUDY PROCEDURES

### 6.1 Pre Visit Evaluation

Eligible subjects will be identified for inclusion at the time of referral. The study coordinator or departmental research staff will confirm compliance with initial inclusion and exclusion criteria. Informed consent will then be obtained. Then initial screening documentation, including THI, TFI, Tinnitus VAS-A and VAS-L, GAD7, GHQ, PHQ8, NEO-PI, and patient history will be reviewed.

If the patient is being seen in the Otolaryngology clinic for an alternative chief complaint, but a screening review of systems identified significant tinnitus, one of the members of the research team will be available for screening consultation and may provide informed consent at that time. A copy of the consent form will be provided to the patient to keep, and a copy will be filed and stored. Once enrolled, the THI, TFI, Tinnitus VAS-A and VAS-L, GAD7, GHQ, PHQ8 and NEO-PI scores of the subject will be recorded by the research staff.

If the patient is unable to schedule a Pre Visit Evaluation, consent may then be mailed (either via the postal service or electronically through PTRAX) to the patient. The consenting provider will meet with the patient by phone or video visit and read through the consent form with the potential participant. If desire to proceed, signed consent form will be returned either electronically or by mail and screening documentation will be provided to the patient. The THI, TFI, Tinnitus VAS-A and VAS-L, and Pain VAS, GAD-7, PHQ-8, and/or the NEO-PI may be mailed or sent electronically to the subject after consent so they may do these eligibility screening surveys at home without making a trip to Mayo Clinic. They will return these screening surveys which will be scored, and if the scores qualify, the subject will come in person for a clinical visit and the rest of the initial screening surveys, if they did not do the whole set at home.

After eligibility is determined, subject will complete study questionnaires (THI, TFI, and Tinnitus VAS-A and VAS-L) at three separate time periods in conjunction with the first clinical visit.

### 6.2 First Clinical Visit

1. Patients enrolled in the study will proceed to Mayo Clinic Otorhinolaryngology Department for additional evaluation. Candidate subjects will undergo a temporal bone CT, contrast enhanced head MRI, audiogram with immittance testing, pitch and level matching of tinnitus, and DPOAE and ABR testing prior to promontory stimulation. If during the course of the patient's visit, any of the exclusion criteria are met, the patient will be withdrawn from the study, and will be notified of this as soon as possible. If the patient has already had a temporal bone CT and/or a head MRI, they do not need to get another for this study.
  - a. The number and estimated length of each study visit

- i. 5 visits in total. The first visit would include a ~30 minute overview. The next visit would require ~2 min temporal bone CT, ~45 min MRI with contrast, ~45 min ABR, ~45 min audiogram and DPOAE, ~30-60 min of stimulation. The next 2 visits would require ~30-60 min stimulation. The last visit would require ~20 min for tympanic membrane evaluation for residual perforation and ~45 min for audiogram.

#### **6.2.1 Transtympanic Cochlear Promontory Stimulation**

- a. At the first, second and third clinical appointment, the promontory stimulation equipment (Cochlear Corporation Nucleus Promontory Stimulator Z10012®; Cochlear Corporation, Melbourne, Australia) will be used. The initial session of promontory stimulation will define optimal stimulation parameters (i.e., current level, and frequency), where maximal tinnitus suppression occurs with minimal or no auditory percept. Stimulus amplitude will be increased slowly to establish threshold and maximum acceptable loudness. As an internal control function, testing will include a run of “on-off” simulations blinded to the subject, with patient blinded status to the “off” or “on” position of the stimulation machine. After these parameters are established, the patient will complete the THI, TFI, and VAS immediately prior to stimulation, during stimulation, and following completion of stimulation at 10-minutes, 1-hour, 24-hours, 48-hours, and 1-week following completion of stimulation (or prior to the next scheduled session of promontory stimulation, whichever occurs sooner), in addition to the recall survey, which is completed after a time period of one week (or prior to the next scheduled session of promontory stimulation, whichever occurs sooner). In addition, pitch and level matching of tinnitus will be completed immediately prior to the first promontory stimulation session and after the last session. Each patient will undergo three successive treatments separated by 7 days (+14/- 2 days). Prior to each treatment, the patient will receive an audiogram and DPOAE testing to document interval safety. At the conclusion of the study, subjects will be asked about their willingness to undergo surgical implantation of a device capable of long-term scheduled or on-demand electrical stimulation for tinnitus suppression.
- b. The Cochlear Corporation Nucleus Promontory Stimulator Z10012 (Cochlear Corporation, Melbourne, Australia) will deliver stimulatory electric pulses. The stimulation will be delivered to the target sites using a transtympanic electrode kit, which contains a monopolar transtympanic needle electrode referenced to a surface electrode to be placed on the patient’s forehead. The tympanic membrane will be visualized with otomicroscopy with the patient in the supine position. Phenol will be applied to the tympanic membrane for local anesthesia. If residual irritation is perceived, EMLA cream will be used in the external auditory canal. The transtympanic electrode needle will be guided through the external canal aiming for the posteroinferior quadrant of the tympanic membrane. The needle will be stabilized in the ear canal using cotton packing or hearing aid mold putty and adhesive tape. Initially, an electrode impedance test will be performed

to validate proper placement and electrical contact of the electrodes. An indicator light will denote when impedances are not acceptable. If impedance values are not acceptable, a gentle repositioning of the proximal end of the needle electrode may be employed to ensure proper placement on the promontory. Otherwise, the needle electrode will be removed and reintroduced. Once proper electrical contact is validated, a calibration session to assess optimal stimulation parameters for the therapeutic session will be carried out using a range of 0 to 1 mA for pulse frequencies 100 Hz, 800 Hz and 1600 Hz. For each stimulus frequency, current level will be gradually increased to determine the following perceptual parameters: 1) Detection threshold or minimum threshold: first detection of the electrical stimulus (tactile or audible) as reported by the patient. 2. Maximum acceptable loudness level or discomfort level: when the applied current is perceived as loud but not uncomfortable. 3. The effective stimulation level will be determined to be 80% of the discomfort level or at minimum the minimum threshold level. The total duration of the electrical stimulation (at the optimal level) in each session will be ~30-60 minutes.

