### 4 STUDY DESIGN

#### 4.1 General Design

1. Experimental approach: adult patients with normal to moderate hearing loss and disruptive intractable asymmetric tonal tinnitus will be recruited for electrical promontory stimulation testing.
2. Candidate subjects will undergo a temporal bone Computed Tomography (CT) scan, contrast enhanced head Magnetic Resonance Imaging (MRI), audiogram with immittance testing, pitch and level matching of tinnitus, Distortion Product Otoacoustic Emissions (DPOAE) and Auditory Brainstem Response (ABR) testing prior to promontory stimulation. Head MRI, DPOAE, audiogram and immittance testing are considered clinically routine for assessment of asymmetric tinnitus. Temporal bone CT, ABR, tinnitus pitch, level matching, masking levels and residual inhibition testing are not standard clinical assessments for asymmetric tinnitus. In addition, subjects will complete the Tinnitus Handicap Inventory (THI), Tinnitus Functional Index (TFI) and Tinnitus Visual Analog Scale (VAS)-L (loudness) and Tinnitus VAS-A (annoyance) questionnaires three separate times within the 10 days prior to promontory stimulation testing. Additional testing for comorbid anxiety and depressive conditions will be a screening Generalized Anxiety Disorder (GAD7), Patient Health Questionnaire (PHQ8), and short Health Anxiety Inventory (HAI-S). The NEO Personality Inventory (NEO PI) will be administered to provide baseline information. The initial session of promontory stimulation will define safety stimulation parameters, with a continual treatment after defining these parameters. After treatment is completed, the patient will complete the THI, TFI, and Tinnitus VAS-A and Tinnitus VAS-L immediately prior to stimulation, during stimulation, and following completion of stimulation at 10-minutes, 1-hour, 24-hours, 48-hours, and 1-week (or prior to the next scheduled stimulation treatment, whichever occurs first) following completion of stimulation. There will also be a “recall survey” in which patients will recall the time and feeling that their tinnitus felt in the week after the stimulation procedure. In addition, pitch and level matching of tinnitus will be completed prior to the first promontory stimulation session and after the last session. Each patient

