#### **4.3 Secondary Study Endpoints**

The secondary study endpoints include determining treatment parameters of the cochlear promontory for maximum tinnitus suppression.

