#### b Data Analysis

THI, TFI and Tinnitus VAS scores will be analyzed based on numeric change over time after each promontory stimulation procedure. Data from the Audiograms / DPOAE will be assessed to ensure no baseline change in hearing has occurred as safety precautionary measures.

The NEO PI will be evaluated to determine correlation between tinnitus improvement scores and baseline personality assessment. Results of the NEO PI will not be used to screen for enrollment.

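### Settings are to be chosen for tinnitus suppression, but no tinnitus rating is scheduled during calibration and no analysis compares settings

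*Combined protocol and SAP*

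**What the plan says.** Section 6.2.1 (a) sets the aim of the initial session, which is to define "optimal stimulation parameters (i.e., current level, and frequency), where maximal tinnitus suppression occurs with minimal or no auditory percept". Its next sentence is about perception only: "Stimulus amplitude will be increased slowly to establish threshold and maximum acceptable loudness".

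Section 6.2.1 (b) gives the working steps. Calibration is carried out "using a range of 0 to 1 mA for pulse frequencies 100 Hz, 800 Hz and 1600 Hz". At each frequency, "current level will be gradually increased to determine the following perceptual parameters", namely a detection threshold (felt or heard) and a level that is loud without being uncomfortable. The level rule follows: "The effective stimulation level will be determined to be 80% of the discomfort level or at minimum the minimum threshold level".

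Section 4.1 describes the same session in other terms: "The initial session of promontory stimulation will define safety stimulation parameters, with a continual treatment after defining these parameters".

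Section 4.3 gives the secondary endpoint as "determining treatment parameters of the cochlear promontory for maximum tinnitus suppression". Section 7.2 b gives the analysis: "THI, TFI and Tinnitus VAS scores will be analyzed based on numeric change over time after each promontory stimulation procedure". It names no factor for frequency or current level.

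**The concern.** The stated criterion is how far tinnitus falls, but the quantities recorded in calibration describe how the stimulus itself is perceived. An operator who follows 6.2.1 (b) finishes calibration with a threshold and a loudness limit at each of three frequencies. Nothing recorded shows which frequency suppressed tinnitus most. Two operators could deliver different frequencies to the same patient and both be following the text.

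The secondary endpoint is at stake. It asks which settings suppress tinnitus best, yet scheduled tinnitus scores would exist only for the setting that was delivered. Ratings not taken during calibration cannot be recovered later.

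**Working it through.** **Part 1: the text side by side**

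1. Criterion: maximal suppression with minimal or no auditory percept, for both current level and frequency (6.2.1 a).
2. Recorded in calibration: detection threshold and maximum acceptable loudness, per frequency (6.2.1 b). No tinnitus measure is listed.
3. Tinnitus scoring: 6.2.1 (a) places THI, TFI and VAS after the parameters have been established, from just before stimulation to one week after. Pitch and level matching is done only before the first session and after the last. Section 7.1 adds no calibration rating.
4. Blinded on-off run (6.2.1 a): it contrasts stimulation with none, not one setting with another, and no outcome is named for it.
5. Analysis (7.2 b): change over time, hearing safety, and correlation with the NEO PI. Nothing is analysed by setting.

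So in each session three frequencies are tried, but scheduled tinnitus scores are taken at the delivered setting only. Settings can be compared only between patients, or between sessions if the setting changes, and in neither case is the setting assigned at random.

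**Part 2: illustrative precision**

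The plan gives no figure for comparing settings and no between-setting effect or SD, so results are in SD units.

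Inputs: n = 24 (7.2 a) and n = 100 (Study Summary); three frequencies (6.2.1 b). Assumptions: equal SDs, and within-patient correlation r = 0.3, 0.5 or 0.7.

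The 24 itself reproduces. With true change 15, threshold 7, SD 15, one-sided 0.05 and 80% power, the one-sample t calculation gives 24. The normal approximation gives ((1.645 + 0.842) × 15/8)² = 21.7, rounded up to 22.

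Standard error of a difference between two frequencies:

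- Across patients, split equally over three: SD × √(2/(n/3)) = SD × √(6/n)
- Across patients, split equally over two: SD × √(2/(n/2)) = SD × √(4/n)
- Within patients: SD × √(2(1 − r)/n)

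The ratios of across-patient to within-patient standard error do not depend on n or alpha:

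| r | three-way split, √(3/(1 − r)) | two-way split, √(2/(1 − r)) |
|---|---|---|
| 0.3 | 2.07 | 1.69 |
| 0.5 | 2.45 | 2.00 |
| 0.7 | 3.16 | 2.58 |

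With 80% power and two-sided 0.05 (multiplier 1.960 + 0.842 = 2.802), the smallest detectable difference is:

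| | n = 24 | n = 100 |
|---|---|---|
| Across, three-way | 2.802 × 0.500 = 1.40 SD | 2.802 × 0.245 = 0.69 SD |
| Across, two-way | 2.802 × 0.408 = 1.14 SD | 2.802 × 0.200 = 0.56 SD |
| Within, r = 0.3 / 0.5 / 0.7 | 0.68 / 0.57 / 0.44 SD | 0.33 / 0.28 / 0.22 SD |

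The plan's only alpha is one-sided 0.05. Using it would lower every entry by the same factor and leave the ratios unchanged.

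**Part 3: selection and time**

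The expected maximum of three independent standard normal values is 0.846. Picking the best of three equally effective settings from single ratings therefore overstates the fall by about 0.85 rating SD.

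Three frequencies plus one 'off' run make four rated runs with three pauses. At an assumed 1 to 2 minutes each, that is 4 + 3 = 7 to 8 + 6 = 14 minutes.

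**The case against.** **The two items form one procedure.** They are (a) and (b) of a single section, and (b) takes up the idea of optimal parameters from (a). The first can supply the criterion and the second the permitted range, from threshold to 80% of the discomfort level. A threshold-level or purely tactile percept could satisfy both. This stands. A reader might infer that the plan contradicts itself, or that it sets the treatment by loudness and ignores suppression; the documents do not support that. A criterion for frequency exists, but no measure with which to apply it. Nor is the word 'safety' in 4.1 a conflict, since one session can define parameters that are both safe and optimal.

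**The clinician will simply ask the patient.** Probably so. But no instrument, time point or decision rule is given, and 7.1 does not list the answer among the data, so it would be neither standardised nor available for analysis.

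**The precision figures answer a different question.** Section 3 hypothesises an optimum region individual to each patient, whereas the figures concern mean differences between frequencies. They also assume one SD, although a single short rating is likely to be noisier than a scheduled session score. Both points stand, so the figures are illustrative only. But an individual optimum is even harder to find from scores at one setting per patient.

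**More calibration could harm the primary endpoint.** Under 6.2.1 (a) the pre-stimulation scores follow calibration, and Section 1 reports residual inhibition lasting hours to days in some patients. Extra rated runs before that baseline could lower it and shrink the measured change. This stands, and the fix has to deal with it.

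**Conclusion.** The point holds in a limited form. The plan states a suppression criterion for current level and frequency but schedules no tinnitus measure during calibration to apply it, and plans no comparison by setting. As written, the secondary endpoint would rest on scores at the delivered setting, compared across non-randomised patients or sessions.

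On size, a within-patient comparison would have a standard error 2.1 to 3.2 times smaller than a three-way split across patients, or 1.7 to 2.6 times smaller than a two-way split. This rests on equal SDs and r between 0.3 and 0.7, neither of which the documents supply. It would also remove confounding by patient.

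Two stronger conclusions might be drawn and are not supported. One is that the trial can learn nothing about settings: comparisons across patients or sessions remain possible, though unplanned and confounded. The other is that the efficacy result is compromised: the primary analysis of change after stimulation does not depend on how the setting was chosen. This is a cheap improvement, not a flaw that endangers the trial.

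**What to change.** 1. In 6.2.1, state that the suppression criterion in (a) governs within the threshold-to-80% range in (b). Align the wording of 4.1.
2. In the existing calibration, record VAS-L and stimulus loudness once at each of the three frequencies, at the level given by (b), and also in the blinded 'off' run. Pause briefly between runs and rotate frequency order across patients.
3. Deliver the frequency with the largest VAS-L fall among those at or below a stimulus-loudness cut fixed in advance. Name a default for patients in whom no setting lowers VAS-L. State whether sessions 2 and 3 reuse the setting.
4. Take the pre-stimulation THI, TFI and VAS before calibration, so that residual inhibition from calibration does not lower the primary baseline.
5. Add the ratings to 7.1, and to 7.2 b an exploratory within-patient comparison of VAS-L by frequency.

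The cost is a protocol amendment and about 7 to 14 extra minutes per calibration with the needle in place, against roughly 30 to 60 minutes of stimulation. No new visit, device or current range is needed. Single short ratings are noisy and may reflect masking or carry-over between runs. The selected setting's fall will look too large, by about 0.85 rating SD if the three are in truth equal; the VAS already scheduled during stimulation re-checks it. The change does nothing for the promontory-region objective in the Study Summary and Section 3.

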Promontory stimulation is an established otologic procedure that was initially developed as a diagnostic tool to assess patient candidacy for cochlear implantation. Promontory stimulation is most commonly performed in the outpatient setting on an awake patient by placing a single insulated probe through a topically anesthetized tympanic membrane and applying monopolar current for several seconds to minutes. The safety and efficacy of *transtympanic* promontory stimulation for the temporary relief of tinnitus in patients with normal hearing and varying degrees of hearing loss has recently been evaluated [3]. Overall, the literature supports that 45% to 86% of subjects gain significant or complete suppression of tinnitus according to different measures and varying stimulation parameters. Furthermore, in most cases, electrical stimulation can be successfully administered with either no perception or only transient and minimal perception [4]. When evaluating the efficacy of tinnitus suppression according to underlying etiology, it has been found that patients with acoustic trauma or noise-induced hearing loss had the highest success rates of tinnitus suppression compared to other etiologies such as presbycusis or Ménière's disease [5]. However, most patients only experience tinnitus suppression during and shortly after active electrical stimulation, with a smaller subset enjoying

residual inhibition for hours to days after treatment [5-6]. Thus, while successful at providing temporary reprieve, the method of *transstympatic* promontory stimulation utilizing an external system does not provide a solution to manage chronic tinnitus. To suppress tinnitus long-term, patients must have access to continuous or repetitive electrical stimulation.

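### The score labelled as immediately before stimulation can fall after the calibration current, and 7.2b does not say which score is the reference for change

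*Combined protocol and SAP*

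**What the plan says.** Section 6.2.1(a) describes the initial session in this order. First comes the parameter search: "The initial session of promontory stimulation will define optimal stimulation parameters (i.e., current level, and frequency), where maximal tinnitus suppression occurs". Next is a blinded control element: "As an internal control function, testing will include a run of" on-off stimulations. Then come the questionnaires: "After these parameters are established, the patient will complete the THI, TFI, and VAS immediately prior to stimulation".

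Section 6.2.1(b) describes the calibration itself. It follows phenol, needle placement and the impedance test, and it "will be carried out using a range of 0 to 1 mA for pulse frequencies 100 Hz, 800 Hz and 1600 Hz". It adds: "For each stimulus frequency, current level will be gradually increased to determine the following perceptual parameters".

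The same score is timed differently elsewhere. Section 4.1 has "After treatment is completed, the patient will complete the THI, TFI, and Tinnitus VAS-A and Tinnitus VAS-L immediately prior to stimulation". Section 7.1 lists a score just before stimulation and does not mention calibration.

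On persistence, Section 1 says that "most patients only experience tinnitus suppression during and shortly after active electrical stimulation", with a smaller subset having "residual inhibition for hours to days after treatment".

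Other scores precede exposure. Section 4.1 requires THI, TFI, VAS-L and VAS-A on three occasions in the 10 days before stimulation testing; 6.1 ties these more loosely to the first clinical visit. Sections 4.1, 6.2.1(a) and 7.1 also collect a score at one week or before the next session, whichever is sooner. Section 7.2b analyses numeric change over time after each procedure and does not say from which score the change is measured.

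**The concern.** Stimulation parameters can only be found by applying current. A score taken once they are found therefore follows active stimulation that was steered towards maximal suppression, and it falls in the period when the protocol itself expects suppression to persist. It is not a clean pre-exposure value, at least in session 1.

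Section 4.2 makes questionnaire-based relief a primary endpoint. The study has no parallel control group, and no analysis of the on-off run is specified. Efficacy therefore rests on within-patient change, and any shift in the reference score passes directly into the result. If calibration has already reduced the tinnitus, the session effect is understated; if it has aggravated it, the effect is overstated. The first is more plausible, because the search aims at suppression. Section 6.2.1(b) describes the so-called discomfort level as loud without being uncomfortable, which gives little support to aggravation.

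**Working it through.** **1. Which sessions are affected.** Section 6.2.1(a) assigns the parameter search to the initial session, so the post-calibration order is explicit only there. Section 6.2.1(b) can be read as calibrating after every needle placement. On the first reading session 1 is affected and sessions 2 and 3 are not; on the second, all three are. That the on-off run comes before the questionnaires is inferred from the order of the sentences; it is not stated.

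**2. What else could serve as reference.** For session 1, the three earlier questionnaires. For sessions 2 and 3, the one-week or pre-next-session score. Sessions are 7 days (+14/−2) apart, that is 5 to 21 days, so the one-week score can be up to 21 − 7 = 14 days old when the next session starts.

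**3. The plan's own sample size.** Inputs from 7.2a: one-sided alpha 0.05, power 80%, true mean THI change 15, SD of change 15, thresholds 7 and 5. Normal approximation: n = [(1.645 + 0.842) × SD / (change − threshold)]².

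- Threshold 7: (2.487 × 15/8)² = 21.7, so 22. The exact one-sample t calculation gives 24, as stated.
- Threshold 5: (2.487 × 15/10)² = 13.9, so 14. Exact t gives 16, as stated.

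**4. Effect of carry-over, if the post-calibration score is the reference.** Let calibration lower the mean pre-score by c THI points, with the final score and the SD unchanged. The measured change is then 15 − c. Power comes from the noncentral t distribution with n − 1 degrees of freedom and noncentrality (15 − c − threshold)/15 × √n. For threshold 7 and n = 24 this is 8/15 × 4.899 = 2.61 at c = 0, and 3/15 × 4.899 = 0.98 at c = 5. The documents give no value for c; the range below is assumed.

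| c (assumed) | Measured change | Power, threshold 7, n = 24 | Power, threshold 5, n = 16 | Power, threshold 7, n = 100 | n for 80%, threshold 7 |
|---|---|---|---|---|---|
| 0 | 15 | 81% | 82% | over 99% | 24 |
| 1 | 14 | 72% | 74% | over 99% | 30 |
| 2 | 13 | 60% | 65% | 99% | 41 |
| 3 | 12 | 48% | 55% | 95% | 58 |
| 5 | 10 | 24% | 36% | 63% | 156 |

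The last entry agrees with the protocol's own table (change 10, SD 15, threshold 7). At n = 100 and threshold 5, c = 5 still leaves 95% power. A larger sample recovers power but not the estimate, which stays c points too small.

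**The case against.** The strongest reply is that no bias has been shown. Section 7.2b names no reference, so an analyst could use the pre-exposure scores that the plan already collects. On the reading that calibration occurs only in session 1, the three earlier questionnaires cover the whole problem. The clause in 4.1 cannot be carried out as written, which suggests that these opening clauses loosely introduce a whole schedule and do not fix an exact order. A score taken after calibration also has a legitimate use: it can isolate the effect of the 30 to 60 minute therapeutic run.

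Most of this stands, and it limits the point. It does not remove it. The plan does not designate the uncontaminated scores, the looser wording in 6.1 leaves it unclear whether the three questionnaires must precede stimulation, and for later sessions the alternative score may be two weeks old. Loose drafting is also a less likely explanation in 6.2.1(a), where pitch and level matching and the audiogram are placed clearly before the session or treatment and only the questionnaires follow parameter-setting.

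A reader might infer that 45% to 86% of patients would already be suppressed when the reference is taken. Section 1 gives that range for treatment studies using different measures and parameters; it is not the share still suppressed after a calibration ramp. A reader might also infer that the required size rises from 24 to 156. That needs 5 points of carry-over, which nothing in the documents establishes, and it ignores the accrual target of 100 in the Study Summary.

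**Conclusion.** The point holds as a conditional one. Read literally, 6.2.1(a) produces a post-exposure score under a pre-stimulation label in session 1, and possibly in all three sessions. Sections 4.1, 6.2.1 and 7.1 disagree on its timing, and 7.2b leaves the reference open. If that score is the reference and carry-over is not zero, the session effect can be biased, most plausibly downwards. The documents do not support the stronger statement that the measured effect is biased, because that needs both conditions.

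The size is unknown. On the assumptions in the working, each THI point of carry-over removes one point from the measured change. At 24 patients and threshold 7, power is 72% at 1 point and 24% at 5; at 100 patients it is 95% at 3 points and 63% at 5. With zero carry-over, or a pre-exposure reference, nothing is lost. This should be fixed; confidence is moderate.

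**What to change.** Reconcile 4.1, 6.2.1(a), 6.2.1(b) and 7.1 so that at every session the pre-stimulation THI, TFI, VAS-A and VAS-L are completed on arrival, before phenol, needle placement and any current. Remove the opening clauses of the two sentences quoted from 6.2.1(a) and 4.1 as they apply to that score. State whether calibration takes place in the first session only or in each session.

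In 7.2b, name this pre-exposure score as the reference for per-session change. Use the mean of the three earlier questionnaires as the overall baseline or in a sensitivity analysis, and align 6.1 with 4.1 so that all three clearly precede stimulation. Keep any post-calibration score as a separately labelled time point.

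The cost is wording and the order of questionnaires within the visit, plus possibly one extra labelled VAS. A pre-exposure score not taken on the day cannot be recovered later.
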